10.3.8.2. Observational Visit 6 / Early Withdrawal Visit for the Observational Cohort

Patients will report to the clinic after having taken their usual PD medications prior to the visit. The timing of administration of the usual morning dose of PD medication may be adjusted by the investigator to accommodate the patient's and/or clinic's schedule. Following their usual morning PD medication, no further PD medications will be used until following completion of all assessments. The timing of arrival should be scheduled to increase the likelihood that patients will be in an ON state upon arrival (i.e., they should arrive to the clinic as shortly as feasible after taking their standard oral PD medications at home). Patients will bring to the clinic all usual PD medications.

The following procedures will be done:

- Confirm that the DLco assessment was performed within 2 weeks prior to OV6. If the DLco assessment has not been completed prior to the visit, the study visit must be re-scheduled.
- Record any changes in the usual PD medication dose/regimen.
- Record any changes in concomitant medications.
- Perform the PDQ-39, UPDRS Part 2, and S&E ADL (each preferably in the ON state and must be before other study evaluations).
- Perform a brief physical examination.
- Record standard vital signs (BP, HR, and RR) and orthostatic vital signs (BP and HR).
- Perform 12-lead ECG.
- Perform spirometry assessment (preferably in the ON state; however, if the patient is not in an ON state, perform the evaluation and record the motor state with each assessment).
- The C-SSRS, Epworth Sleepiness Scale, and QUIP should be completed.
- Collect blood for clinical laboratory tests including serum pregnancy test, if applicable. Document fasting status.
- Monitor patients for AEs.

Once all of the assessments are complete, schedule the patient for a DLco assessment 4 to 5 weeks after OV6. The DLco assessment should be performed while the patient is in an ON state (as reported by the patient to the pulmonary technician) at the pulmonary function facility. As part of the procedure, a slow vital capacity will be performed, followed by DLco, and then spirometry.

10.3.9. Early Withdrawal Visit

Patients in the CVT-301 treatment group who withdraw prematurely will complete the TV6 assessments for the CVT-301 patients (see [Section 10.3.8.1](#)), except for the pre-TV6 DLco assessment, at the time of withdrawal. Patients in the observational cohort who withdraw

prematurely will complete the OV6 assessments for the observational cohort (see [Section 10.3.8.2](#)), except for the pre- OV6 DLco assessment, at the time of withdrawal.

All patients who withdraw early, regardless of treatment group, will be scheduled to undergo a DLco assessment 4 to 5 weeks after completion of the Early Withdrawal Visit. The DLco assessment should be performed in an ON state (as reported by the patient to the pulmonary technician) in the pulmonary function facility. As part of the procedure, a slow vital capacity maneuver will be first, followed by DLco, and then spirometry.

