--	---

	
Clinic staff will confirm that DLco assessment was performed within 2 weeks prior to the visit (and if not, re-schedule study visit). Clinic staff will record any changes in standard PD medication dose/regimen and record the time that patients took their usual PD medications prior to the visit. The following assessments will be performed: recording of any changes in concomitant medications; brief physical examination; standard vital signs (BP, HR, and RR) and orthostatic vital signs (BP and HR); ECG; spirometry (preferably in the ON state); and clinical laboratory tests (with documentation of fasting status) including serum pregnancy test, if applicable.
 
In addition the following assessments will be recorded: the PDQ-39, UPDRS Part 2, and S&E ADL scale (each preferably in the ON state); QUIP; Epworth Sleepiness Scale; and C-SSRS.
 
In addition for the CVT-301 treated group only:
 
Patients will complete the PD Diary for the 3 consecutive days prior to TV6 and the Inhaled Dosing Log daily throughout the treatment period. The clinic staff will review, sign, and date the PD Diary and Inhaled Dosing Log and collect all used and unused supplies. The UPDRS Part 4 (Questions 32-35 and 36-39) will be completed
 
The patient will remain in the clinic until he/she goes into the OFF state. Patients will be provided with a new inhaler for dosing at TV/OV6 and will use study drug from the supplies brought to the visit. In the OFF state, the patient will undergo UPDRS Part 3 assessments, immediately pre-dose, following which the patient will prepare and then self-administer (under staff supervision) the entire dose of inhaled study drug. The dosing time is defined to be when the patient's OFF state is recognized by both the patient and investigator to be at a level similar to the investigator-confirmed severity experienced at SV1 and preferably between 2 and 5 hours after their prior oral PD medication.
 
Exploratory efficacy responses will be assessed by recording: (1) UPDRS Part 3 evaluations at 10, 20, 30, and 60 minutes post-dose; (2) the occurrence and severity of dyskinesia; and (3) whether the patient converted to an ON state during the 60-minute post-dose time period and if so, whether he/she was still in an ON state at 60 minutes post-dose. The PGI-C will be completed, preferably in the ON state and must be done before other study evaluations.
 
All patients:
 
Adverse events will be monitored throughout the visit. Once all of the assessments are complete, patients will be scheduled for a DLco assessment 4 to 5 weeks after TV/OV6. The DLco assessment should be performed while the patient is in an ON state (as reported by the patient to the pulmonary technician) at the pulmonary function facility. As part of the procedure, a slow vital capacity will be performed, followed by DLco, and then spirometry.
 
Patients who withdraw prematurely will complete the TV/OV6 assessments at the time of withdrawal (except the pre-TV/OV6 DLco assessment) and will be scheduled to undergo a DLco

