8.3. Removal of Patients from Study

A patient may withdraw from the study at any time at his/her own request, or may be withdrawn at any time at the discretion of the investigator for safety, behavioral, or administrative reasons. If a patient is discontinued prematurely at any time after entering the study, the investigator will make every effort to see the patient and complete the TV/OV6 assessments as shown [Appendix 14](#) (for patients in the CVT-301 treatment group) or [Appendix 15](#) (for patients in the observational cohort). If a patient is withdrawn due to an AE, the event must be followed, when possible, until resolution.

An end-of-study page in the electronic case report form (eCRF) should be completed for every patient who receives study drug (if in the CVT-301 treatment group) or enters the TV/OV1 visit (if in the observational cohort), whether or not the patient completes the study. The reason for any early discontinuation should be indicated on this form. The primary reason for a patient withdrawing prematurely should be selected from the following standard categories of early termination:

- *Adverse Event:* Clinical or laboratory events occurred that in the medical judgment of the investigator for the best interest of the patient are grounds for discontinuation. This includes serious and non-serious AEs regardless of relation to study medication.
- *Death:* The patient died.
- *Withdrawal of Consent:* The patient desired to withdraw from further participation in the study in the absence of an investigator-determined medical need to withdraw. If the patient gave a reason for withdrawing, it should be recorded in the eCRF.

- *Protocol Violation*: Significant findings indicating that the study investigator or patient failed to adhere to the protocol requirements (e.g., drug noncompliance, failure to return for defined number of visits). The violation necessitated premature termination of the patient from the study.
- *Lost to Follow-Up*: The patient stopped coming for visits, and study personnel were unable to contact the patient.
- *Other*: The patient was terminated for a reason other than those listed above (to be specified on the eCRF).

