10.3.8.1. Treatment Visit 6 / Early Withdrawal Visit for the CVT-301 Treatment Group

Patients will complete the PD Diary for the 3 consecutive days prior to TV6 and the Inhaled Dosing Log daily up until TV6. Patients will bring their usual PD medications, the PD Diary, Inhaled Dosing Log, used supplies including empty capsules and inhalers, as well as any unused supplies to the clinic visit.

Patients will report to the clinic after having taken their usual PD medications prior to the visit. The timing of administration of the usual morning dose of PD medication may be adjusted by the investigator to accommodate the patient's and/or clinic's schedule. Following their usual morning PD medication, no further non-study PD medications will be used until following completion of all assessments. The timing of arrival should be scheduled to increase the likelihood that patients will be in an ON state upon arrival (i.e., they should arrive to the clinic as shortly as feasible after taking their standard oral PD medications at home). Patients will bring to the clinic all usual PD medications.

The following procedures will be done:

- Collect, review, sign, and date the PD Diary and Inhaled Dosing Log.
- Collect used empty capsules and inhalers and unused supplies.
- Confirm that the DLco assessment was performed within 2 weeks prior to TV6. If the DLco has not been completed prior to the visit, the visit must be rescheduled.
- Record any changes in the usual PD medication dose/regimen.
- Record the time that patients took their usual PD medications prior to the visit.
- Record any changes in concomitant medications.

- Perform the PDQ-39, PGI-C, UPDRS Part 2, and S&E ADL (each preferably in the ON state and must be done before other assessments).
- Patients will complete the UPDRS Part 4 (Questions 32-35 and 36-39).
- Perform a brief physical examination.
- Record standard vital signs (BP, HR, and RR) and orthostatic vital signs (BP and HR).
- Perform a 12-lead ECG.
- The C-SSRS, Epworth Sleepiness Scale, and QUIP should be completed.
- Perform spirometry assessment (preferably in the ON state; however, if the patient is not in an ON state, perform the evaluation and record the motor state with each assessment).
- Collect blood for clinical laboratory tests including serum pregnancy test, if applicable. Document fasting status.

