- The patient will remain in the clinic until they go into the OFF state. After confirmation of an OFF state (between 2 and 5 hours after the patient has taken his/her oral PD medication), record the time of the OFF state and then perform a pre-dose UPDRS Part 3 assessment. Under clinic staff supervision, patients will prepare and self-administer their entire dose of inhaled CVT-301. The dosing time is defined to be when the patient's OFF state is recognized by both the patient and investigator to be at a level similar to the investigator-confirmed severity experienced at SV1 and preferably between 2 and 5 hours after their prior oral PD medication. A new inhaler will be provided for this dose, and patients will use study drug from the supplies brought to the visit.
- Perform serial UPDRS Part 3 assessments at 10, 20, 30, and 60 minutes post-dose.
- Observe the patient for the appearance of dyskinesia and note in the eCRF if the patient experiences dyskinesia at any time within the 60-minute post-dose period. Also, if applicable, record the maximum severity of dyskinesia during the 60-minute post-dose period.
- Observe the patient for the occurrence of an ON state during the 60-minute post-dose period and note whether this occurs. If the patient converts to the ON state, note whether or not the patient is still in the ON state at 60 minutes post-dose.
- Monitor patients for AEs throughout the visit.

Once all of the assessments are complete, schedule the patient to undergo a DLco assessment 4 to 5 weeks after completion of TV6. The DLco assessment should be performed in an ON state (as reported by the patient to the pulmonary technician) in the pulmonary function facility. As part of the procedure, a slow vital capacity maneuver will be first, followed by DLco, and then spirometry.

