APPENDIX 13: TIME AND EVENTS TABLE—OBSERVATIONAL VISIT 5 (OV5) (9 MONTHS [36±2 WEEKS] AFTER OV1)

Procedures	Assess in Either ON or OFF State Unless Otherwise Noted	End of OV5	Post- OV5 Telephone Contact
Confirm DLco assessment ¹ has been performed prior to visit; and if not complete, re-schedule study visit	X		X
Record any changes in usual PD medication dose/regimen	X		
Record any changes in concomitant medications	X		
Physical examination (brief)	X		
Vital signs (standard BP, HR, and RR and orthostatic BP and HR)	X		
Spirometry (preferably in ON state)	X (ON)		
Clinical laboratory tests (serum pregnancy test, if applicable)	X ²		
C-SSRS	X		
Monitor for AEs		X	
Schedule next visit		X	
Schedule DLco visit at pulmonary site (14±3 days before next visit)		X	
Post- OV5 telephone contact: call patient 2 weeks (± 3 days) before OV6			X

¹DLco is to be performed in a dedicated pulmonary facility and includes slow vital capacity maneuver, DLco, and spirometry. Preferably in the ON state.

²Document whether patient is fasting (≥4 hours after last snack or meal).

APPENDIX 14: TIME AND EVENTS TABLE—TREATMENT VISIT 6 (TV6) (12 MONTHS [52±2 WEEKS] AFTER TV1)/EARLY WITHDRAWAL VISIT

Procedures	Arrival	Pre-dose	Time 0 (Dosing)¹	10 min Post-dose	20 min Post-dose	30 min Post-dose	60 min Post-dose	End of TV6	Post-TV6 Assessments
Collect, review, sign, and date PD Diary and Inhaled Dosing Log	X								
Collect empty capsules, inhalers, and unused supplies	X								
Confirm DLco assessment ² has been completed prior to visit; if not done, the study visit must be re-scheduled ³	X								
Record any changes in usual PD medication dose/regimen	X								
Record time of patient's prior usual PD medication dose	X								
Record any changes in concomitant medications	X								
PDQ-39 (preferably in ON state)	X ⁴								
PGI-C (preferably in ON state)	X ⁴								
UPDRS Part 2 (preferably in ON state)	X ⁴								
S&E ADL (preferably in ON state)	X ⁴								
UPDRS Part 4 (Questions 32-35 and 36-39)	X								
Physical examination (brief)	X								
Vital signs (standard BP, HR and RR and orthostatic BP and HR)	X ⁵								
Electrocardiogram	X								
C-SSRS	X								
Epworth Sleepiness Scale	X								
QUIP	X								
Spirometry (preferably in ON state)	X								
Clinical laboratory tests (including serum pregnancy test, if applicable)	X ⁶								
Provide new inhaler for treatment		X							
UPDRS Part 3		X ⁷		X	X	X	X		
Self-administration of study drug (in OFF state)			X ¹						

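### The Early Withdrawal Visit includes a supervised CVT-301 dose, with no waiver when study drug was already stopped for an adverse event or other safety reason

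*Protocol*

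**What the plan says.** Section 10.3.9 states that patients in the CVT-301 group "who withdraw prematurely will complete the TV6 assessments for the CVT-301 patients", "except for the pre-TV6 DLco assessment, at the time of withdrawal". The synopsis has the same rule and the same single exception: "Patients who withdraw prematurely will complete the TV/OV6 assessments at the time of withdrawal". Appendix 14 footnote 3 repeats it.

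Section 10.3.9 points to Section 10.3.8.1, whose title covers both TV6 and the Early Withdrawal Visit. There the patient stays in clinic until OFF, takes no further non-study PD medication until assessments are finished, and has a pre-dose UPDRS Part 3. Then, under supervision, "patients will prepare and self-administer their entire dose of inhaled CVT-301". UPDRS Part 3 follows at 10, 20, 30 and 60 minutes, with observation for dyskinesia and the ON state over the same hour. Appendix 14, also headed for both visits, marks self-administration of study drug at Time 0 and attaches no early-withdrawal exemption to that row.

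Section 8.3 asks the investigator to "make every effort to see the patient and complete the TV/OV6 assessments as shown" in Appendix 14 for any premature discontinuation of a CVT-301 patient. For an adverse event withdrawal it adds only that the event be followed, where possible, to resolution.

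**The concern.** One procedure list serves two kinds of patient. A completer at month 12 is still using CVT-301, and one more in-clinic dose changes nothing. A patient taken off CVT-301 because of an adverse event or another safety judgement is in a different position. For that patient the same list schedules renewed exposure to the product that was just stopped.

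The return is modest. The dose supports the exploratory UPDRS Part 3 and ON-state endpoints and one secondary objective, examiner-rated dyskinesia after in-clinic dosing (Section 6). It adds nothing to the primary objective, because TV6 spirometry is an arrival item.

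The scheduled checks after the dose are also limited. In Appendix 14, spirometry, ECG and vital signs come at arrival, and vital signs must be completed before dosing. After dosing the schedule lists only UPDRS Part 3, dyskinesia and ON/OFF observation, and adverse event monitoring. At TV1, by contrast, blood pressure and heart rate are repeated at 20 and 60 minutes, and respiratory rate at 10, 20, 30 and 60 minutes.

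**Working it through.** The question is mainly one of text.

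1. **Is there a dosing step that applies to early withdrawal?** Yes, in two places: Section 10.3.8.1 and Appendix 14. Both headings name the Early Withdrawal Visit.

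2. **What is exempted?** Section 10.3.9, the synopsis and Appendix 14 footnote 3 each exempt one item, the pre-TV6 DLco. None exempts the dose.

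3. **Can the listed assessments be done without the dose?** Not all of them. UPDRS Part 3 at 10 to 60 minutes after dosing, the 60-minute dyskinesia observation and the ON-state observation all presuppose it.

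4. **Is the dose waived elsewhere?**
   - Section 8.3 covers withdrawal for safety and for adverse events, but adds only follow-up of the event.
   - The investigator's discretion over which assessments to perform, in Sections 7, 10.3 and 10.3.10, concerns dose reduction for tolerability, not withdrawal.
   - Section 11.1.5 withdraws pregnant patients from further treatment. It covers no other reason.

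5. **Size of the dose** (Section 9.1, Tables 1 and 2; Section 7):
   - full dose: 2 × 25 mg = 50 mg LD FPD
   - reduced-dose kit: 2 × 17.5 mg = 35 mg LD FPD
   - temporary single capsule: 1 × 25 mg = 25 mg LD FPD

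6. **How many patients?** The protocol does not say. Section 12.1 plans 250 CVT-301 patients, about 25% drop-out and 188 completers. Expected drop-outs are 250 − 188 = 62, which agrees with 0.25 × 250 = 62.5. That is an upper bound for all causes. It includes deaths, losses to follow-up, withdrawals unrelated to safety, and patients still dosing when they attend. No split by reason is given, so the bound cannot be narrowed.

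**The case against.** The strongest reply is that the rule asks for assessments, not treatment. The protocol elsewhere speaks of assessments and procedures as separate things, Section 11 does not describe dosing as an assessment, and 10.3.8.1 lists the dose under procedures. This shows some ambiguity, but it does not settle the matter. The post-dose assessments need a dose, and where the drafters named something to leave out for early withdrawals, they named only the DLco.

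A second reply is that an investigator who has stopped the drug for safety would not give it again. Section 8.3 asks for every effort, which is not an absolute duty, the patient may decline, and the trial runs under GCP. This stands in part and makes actual re-dosing less likely. It still leaves a site to depart from its written schedule in order to do the sensible thing.

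A third reply is that the group is narrow. This stands. The visit takes place at the time of withdrawal, and patients keep "the Inhaled Dosing Log daily up until TV6", so many may still be dosing and are not re-exposed. The adverse event category in Section 8.3 also includes events unrelated to study medication.

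A reader might infer that every adverse event withdrawal, or all 62 expected drop-outs, would be re-challenged. The documents do not support that, for the reasons just given. Nor do they support the inference that a pregnant patient must be dosed: Section 11.1.5 is the more specific text and reasonably governs, and the visit schedule only lacks a cross-reference to it.

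**Conclusion.** The point holds in a limited form and should be fixed. As written, the Early Withdrawal Visit for CVT-301 patients contains a supervised dose and dose-dependent assessments, and nothing waives them when study drug was already stopped for an adverse event or other safety reason. The consequence is one further dose of 50, 35 or 25 mg LD FPD per affected patient.

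The conclusion rests on reading the visit instruction to include the dose that its own assessments require. The number of patients is unknown. That it is probably small is a judgement from the narrowing conditions, not a figure in the protocol.

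This is a patient-safety drafting gap. It should not be read as a threat to the primary analysis: spirometry is done at arrival, and the sample size statement does not depend on the dose.

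**What to change.** Add the following to Section 10.3.9, the synopsis, Appendix 14 footnote 3 and the dosing step of Section 10.3.8.1:

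> When study drug was stopped for an adverse event, other safety reason or pregnancy (Section 11.1.5), the following are omitted at the Early Withdrawal Visit: the wait for the OFF state, the associated hold on usual PD medication, the pre-dose UPDRS Part 3, in-clinic study-drug dosing, and all post-dose items (UPDRS Part 3 at 10–60 minutes, dyskinesia and ON-state observation). All arrival items, including spirometry and UPDRS Part 4, as well as AE monitoring and the DLco at 4–5 weeks, remain.

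The preparatory steps need to go with the dose. Otherwise a patient withdrawn for safety would be kept off usual medication until OFF, for a pre-dose score with no dose to follow. The waiver also belongs in 10.3.8.1, because that section is itself headed for the Early Withdrawal Visit.

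The change adds no procedure. Its cost is the loss, in these patients, of one visit's exploratory UPDRS Part 3 and ON-state data and of the examiner-rated dyskinesia observation. That last loss may be selective, since it can fall on patients stopped for dyskinesia. It touches a secondary objective that is characterised descriptively. The dyskinesia questions of UPDRS Part 4 and adverse event monitoring still record dyskinesia at the visit, though they do not replace the post-dose examiner rating.

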10.3.10. Unscheduled Visits

An unscheduled visit may occur when indicated at the discretion of the Investigator. The following are potential circumstances for unplanned visits:

- If concordance is not reached during SV1, the same training and testing may be repeated at an unscheduled visit between SV1 and SV2 or at SV2. If patients return for an unscheduled visit between SV1 and SV2 for concordance training and testing, the visit must occur more than 3 days prior to SV2.
- If a patient is unable to complete a screening assessment at SV2 (repeat SV2), an additional visit may be scheduled prior to eligibility determination and randomization. Any repeat assessments should be performed in the respective motor state as described for SV1.
- If a patient develops significant tolerability concerns that in the opinion of the investigator are of a severity that should necessitate a reduction in dose, including, but not limited to, exacerbation or worsening of troublesome dyskinesia, other problematic dopaminergic symptoms, or other tolerability concerns, a dose reduction (from 2- to 1-capsule inhalation per dose) will be permitted. The medical monitor should be contacted, and the investigator should use his/her clinical judgment to determine if an additional unscheduled visit is required and what assessments should be performed (e.g., physical examination, spirometry, etc.).

